**Does Low Flow Anesthesia Affect Cerebral Oxygenization in Bariatric Surgery?
Prospective Randomized Clinical Study**

[name], Asst. [name] of Anesthesiology and Reanimation, Inonu University Medical Faculty, Malatya, Turkey

[name], Asst. [name] of Anesthesiology and Reanimation, Inonu University Medical Faculty, Malatya, Turkey

Address all correspondence to:

[name], Asst. [name] of Anesthesiology and Reanimation, Inonu University Medical Faculty, Malatya, Turkey

Mail: [contact]

[contact]

Keywords: Bariatric surgery, low flow anesthesia, bispectral index, regional cerebral oxymetry

Does Low Flow Anesthesia Affect Cerebral Oxygenization in Bariatric Surgery? Prospective Randomized Clinical Study

Study Protocol

This study will perform in 60 adult patients who undergoing laparoscopic sleeve gastrectomy or gastric bypass surgery. Morbidly obese patients with ASA (American Society of Anesthesiology) score I-III, aged 18-65 years, BMI > 35 will include in the study. Patients with ASA IV, under 18 years, over 65 years, obstetric patients, uncontrolled diabetes mellitus, cardiovascular and pulmonary disease, cerebrovascular disease and patients who refused informed consent forms will exclude from the study.

Heart rate (HR), noninvasive blood pressure, electrocardiogram (ECG) and peripheral oxygen saturation (SpO₂), monitoring will perform to all patients in operation room without premedication. In addition, regional cerebral oxygen saturation (Near-infrared spectroscopy system, NIRS, INVOS 4100 Cerebral Oximeter, Software Version 7.2.5.0, Somanetics Corporation) and BIS (Bispectral Index, VISTA™ Monitoring System) monitoring will perform to all patients. Two cerebral sensors of NIRS and BIS sensors will glue to the right and left frontal areas under the hairline and covered with tape to prevent exposure to light.

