After preoxygenation (100% 4 L/min O₂ for 3 minutes), propofol (1-2 mg/kg), rocuronium (0.8 mg/kg) and fentanyl (0.1 µg/kg) will administer in anesthesia induction via intravenous route at doses calculated according to ideal body weights. Randomly select patients will divide into two groups: Group L: low flow desflurane and group N: normal flow desflurane. Initially, anesthesia maintain with desflurane inhalation with a flow of 2 L/min in 0.5 O₂ oxygen-air mixture in both groups. While target minimum alveolar concentration (MAC) was 1-1.5 and BIS values are 40-60 concurrently, the flow rate adjust to 0.75 L/min in Group L and 1.5 L/min in Group N. Age-related MAC values will determine and express as a percentage of volume. The ventilation parameters will adjust to maintain the end-tidal carbon dioxide (EtCO₂) values at 35-45 mmHg. Neuromuscular blocker will administer based on Train of Four (TOF, Datex-Ohmeda) values.

HR, SpO₂, EtCO₂, mean arterial pressure (MAP), BIS values, left regional cerebral oxygen saturations (LrSO₂) and right regional cerebral oxygen saturations (RrSO₂) will record at before anesthesia (T₀), after intubation (T₁), before insufflation of CO₂ (T₂), after insufflation of CO₂ (T₃), after reverse trendelenburg position (T₄), after supine position (T₅), after desufflation of CO₂ (T₆), after awakening from anesthesia (T₇). Also anesthesia and surgery times, perioperative and postoperative complications will record. Postoperative analgesia was achieved in all patients with appropriate doses of tramadol and paracetamol via intravenous route.

Does Low Flow Anesthesia Affect Cerebral Oxygenization in Bariatric Surgery? Prospective Randomized Clinical Study

Statistical Analysis

Statistical analysis will carry out by using SPSS program (SPSS for Windows version 22). T-test and Chi-Square Test will be used for the comparison between groups. Correlation analysis will be based on the calculation of Pearson's rank correlation coefficients. Value of p below 0.05 will be considered as statistically significant. Consent to conduct the study was obtained from Local Ethic Committee of Inonu University.

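### rSO2 is recorded on two sides at eight times, but no single comparison is designated as the answer and the pre-anesthesia T0 reading has no role in the analysis

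*Combined protocol and SAP*

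**What the plan says.** The question is the title: "Does Low Flow Anesthesia Affect Cerebral Oxygenization in Bariatric Surgery". The Study Protocol section gives the size ("This study will perform in 60 adult patients") and the allocation ("Randomly select patients will divide into two groups"), with no ratio stated. Both groups start at the same flow. Once MAC and BIS targets are met, "the flow rate adjust to 0.75 L/min in Group L and 1.5 L/min in Group N".

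Among the measurements, "left regional cerebral oxygen saturations (LrSO₂) and right regional cerebral oxygen saturations (RrSO₂) will record" at eight points, beginning "before anesthesia (T₀), after intubation (T₁), before insufflation of CO₂ (T₂") and ending after awakening (T7).

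On group comparisons, the Statistical Analysis section says "T-test and Chi-Square Test will be used for the comparison between groups" and "Value of p below 0.05 will be considered as statistically significant". It adds a correlation analysis without naming the variables. It names no primary outcome, side, time point, average or change score for rSO2. It mentions no baseline adjustment, multiplicity rule or confidence interval.

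**The concern.** Two sides at eight times give 16 rSO2 readings per patient, and any of the 14 after T0 could be put forward as the answer to the title question. With no comparison fixed in advance, one p-value below 0.05 among many could be reported as an effect of low flow, and a reader could not tell what error rate stands behind it.

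The second gap is T0. It is taken before anesthesia, so the flow difference cannot affect it. That makes it a proper baseline covariate, already collected, which the plan leaves unused.

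The third gap is smaller. A non-significant t-test reported by its p-value alone would not show how large a difference the data still allow.

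**Working it through.** **Inputs from the documents.** 60 patients, two groups, threshold 0.05, two sides, eight times. The figure of 60 cannot be reproduced, because no effect size, SD or power is stated.

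**Assumptions, none in the documents.** 1:1 allocation (30 per arm), two-sided tests, SD of 6, 8 or 10 rSO2 points, and the correlations shown below.

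**1. Count.** 2 × 8 = 16 readings. T0 precedes any flow difference, so a test there is a baseline check. That leaves 2 × 7 = 14.

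**2. False-positive chance if all 14 are tested at 0.05.** If the readings were independent it would be 1 − 0.95^14 = 51%. This is only a reference value, because readings within a patient are correlated. Simulation (20,000 trials per setting, 30 per arm, no true difference, equal correlation between times on each side) gives:

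| Correlation between times | Left-right 0.5 | Left-right 0.7 | Left-right 0.9 |
|---|---|---|---|
| 0.3 | 45% | 42% | 37% |
| 0.5 | 38% | 36% | 31% |
| 0.7 | 31% | 28% | 24% |
| 0.9 | 21% | 18% | 16% |

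The range is about 16% to 45%. One designated test has 5%.

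**3. Precision of one reading.** The 95% CI half-width is t × SD × f × √(2/30). Without adjustment, t(58) = 2.002 and f = 1. With T0 as covariate, t(57) = 2.002 and f = √(1 − r²), where r is the correlation of T0 with the outcome.

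| Analysis | SD 6 | SD 8 | SD 10 | Narrowing, 1 − f |
|---|---|---|---|---|
| Unadjusted | 3.10 | 4.13 | 5.17 | – |
| T0-adjusted, r = 0.3 | 2.96 | 3.95 | 4.93 | 5% |
| T0-adjusted, r = 0.6 | 2.48 | 3.31 | 4.14 | 20% |
| T0-adjusted, r = 0.8 | 1.86 | 2.48 | 3.10 | 40% |

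At r = 0.1 the narrowing is 0.5%.

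**4. What an interval adds.** Suppose one unadjusted reading shows an observed 2-point fall at SD 8. The standard error is 8 × √(2/30) = 2.07, so p = 0.34 and the 95% CI is −2 ± 4.13, that is −6.1 to +2.1. The p-value alone hides that a fall of 6 points is still compatible with the data.

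**5. Averaging several readings.** For a T0-adjusted mean of k readings with equal correlation ρ, f = √((1 + (k − 1)ρ)/k − ρ²). With k = 4 and ρ = 0.6, f = √(0.70 − 0.36) = 0.583, and the half-width at SD 8 is 2.41. Without T0, f = √0.70 = 0.837 and the half-width is 3.46, so T0 narrows it by 30%. If correlation decays with each time step (T0, then T3 to T6), T0 narrows the interval for the mean by only about 1% at 0.6 per step and 10% at 0.8 per step.

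**6. What averaging costs.** A 5-point fall at only one of four readings shifts their mean by 5/4 = 1.25 points. With SD 8 and ρ = 0.6, the T0-adjusted mean detects this in about 17% of trials. A T0-adjusted test at that reading detects it in 84%.

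**The case against.** The plan never says which rSO2 variable enters the t-test. A t-test on an average, or on a change from T0, fits its wording, so a single unadjusted reading is only one of the analyses it permits. A t-test also yields a confidence interval as a matter of course. The T0 gain rests on a correlation that the documents do not give. T0 is taken awake and the intraoperative readings under anesthesia, so that correlation could be weak.

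Most of this stands, and it limits the point. The missing commitment to an interval is, on its own, a reporting detail. The T0 gain may be small, and averaging is a choice with a real cost. Two things survive. Silence on which variable is tested is itself the gap. ANCOVA is also the safer use of T0: it is never materially less precise than the unadjusted test, whereas a change score can be. For the mean of four at SD 8, the half-width for a change score is 2.92 against 2.41 for ANCOVA at constant correlation 0.6. With decay of 0.6 per step it is 4.82 against 3.15, and the unadjusted mean itself gives 3.18.

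A reader might infer three stronger things that the documents do not support:
- **That all 14 or 16 tests will be run.** The text allows this but does not commit to it.
- **That p of 0.05 or more will be read as no effect.** No such rule and no equivalence aim is stated.
- **That averaging is worth many extra patients.** The arithmetic 30/0.583² = 88 per arm requires an equal effect at all four readings and constant correlation 0.6. Neither is known here.

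**Conclusion.** The point holds as a gap in specification. Under randomization the t-test is valid, but the plan does not fix which rSO2 comparison it applies to, and it leaves a usable baseline aside. The false-positive chance of about 16% to 45% describes what the plan permits if all 14 post-T0 readings are tested. It rests on assumed between-time correlations of 0.3 to 0.9 and left-right correlations of 0.5 to 0.9. The gain from T0 is 20% of the interval width at r = 0.6 and a few percent or less if r is weak, assuming 30 per arm. This should be corrected before analysis. It does not undermine the design.

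**What to change.** Before analysis, designate one rSO2 comparison. State the side or the left-right average, and either one time point or a summary of several. Choose it to fit the effect the sponsor expects: a single reading if a brief fall at a particular event is expected, an average if a sustained shift is expected. Use readings that the sponsor confirms follow the flow change, since the protocol ties that change to MAC and BIS and not to a numbered time point.

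Analyse that comparison by ANCOVA with the matching T0 value as covariate. Report the Group L minus Group N difference with its 95% CI. Treat the other readings as descriptive or secondary. Interpret p of 0.05 or more through the interval, as no difference detected. A claim of no relevant effect would need a margin and a CI level stated in advance.

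The change needs no new patients or measurements, and SPSS can fit the model. The cost is that the sponsor must commit to one comparison in advance, and an effect confined to other readings would then count only as secondary evidence.

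### Does the mislabelled coefficient, with no stated pairs or time points, undermine the planned correlation analysis?

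*Combined protocol and SAP*

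**What the plan says.** The Statistical Analysis section has one sentence on correlation: "Correlation analysis will be based on the calculation of Pearson's rank correlation coefficients". The decision rule for all tests is "Value of p below 0.05 will be considered as statistically significant", with no mention of sidedness or of adjustment for multiple tests. Group comparisons are handled separately: "T-test and Chi-Square Test will be used for the comparison between groups".

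The Study Protocol section supplies the data that could be correlated. The sample is set by "This study will perform in 60 adult patients". Seven variables are taken repeatedly: heart rate, SpO₂, EtCO₂, MAP, BIS and the left and right cerebral saturations. There are eight recording times, from before anaesthesia (T₀) to "after awakening from anesthesia (T₇"). No passage says which variables are to be correlated, at which time, on what per-patient value, or whether the two groups are combined.

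**The concern.** Two things catch the eye. First, the named coefficient does not exist as written: Pearson's is not a rank method. An analyst must choose, and could in principle choose after seeing both results.

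Second, the bare 0.05 rule sits beside repeated data. If one pair were tested at each of the eight times and any hit reported as a correlation between those variables, the false-positive rate for the pair would be well above 5%. If all 60 × 8 = 480 readings entered one ordinary correlation, readings from the same patient would be counted as independent and the p-value would be too small. At stake is whether a reported significant correlation, say between cerebral saturation and MAP, can be read at the stated level.

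**Working it through.** **Inputs.** From the documents: 60 patients, 8 times, 7 variables, threshold 0.05. Assumed: two-sided tests; normal data except where stated; within-patient correlation (ICC) of 0.3 to 0.9, since the documents give none; no time course shared by the two variables. Unless noted, simulations used 20,000 trials per setting with the two variables truly unrelated.

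**1. The plan's own figure.** One test at 0.05 on 60 independent values has a false-positive rate of 5% by construction. Simulated over ICCs from 0 to 0.9, a single time point gave 4.6% to 5.5% and the patient mean gave 4.5% to 5.0%. The stated level is reproduced.

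**2. Which coefficient.** In 4,000 null datasets of 60 patients, Pearson and Spearman each rejected in 4.85%, and their verdicts differed in 2.8%. Taking whichever is significant therefore gives (4.85 + 4.85 + 2.8)/2 = 6.25%. A separate run of 10,000 gave 6.4% for normal data and 8.0% for log-normal data with log-scale SD 0.6. With a true correlation of 0.3 on the underlying normal scale, the two disagree in 10.8% of datasets (normal), 11.7% (log-scale SD 0.1) and 26.0% (log-scale SD 0.6).

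The last setting implies a coefficient of variation of √(e^0.36 − 1) = 66%. The only ranges in the protocol are much tighter. Reading each as about ±2 SD (an assumption), EtCO₂ of 35–45 mmHg gives 2.5/40 = 6% and BIS of 40–60 gives 5/50 = 10%. The results near normality are the relevant ones for these two variables; no range is given for the others.

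**3. One pair tested at all eight times.** Each test still has its 5%; across ICCs of 0.1 to 0.7 (10,000 runs each) the per-test rate was 4.9% to 5.1%. The chance of at least one hit is 1 − 0.95^8 = 33.7% if the times are independent.

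**4. All 480 readings pooled as independent.** The variance of the correlation is inflated by about 1 + 7 × ICC₁ × ICC₂. At ICC 0.5 in both variables this is 1 + 7 × 0.25 = 2.75, so the effective cut-off is 1.96/√2.75 = 1.18 and the false-positive rate is 23.7%.

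| ICC in both variables | Any of eight times | Pooled, simulated | Pooled, formula |
|---|---|---|---|
| 0.3 | 32.9% | 12.1% | 12.5% |
| 0.5 | 30.8% | 23.4% | 23.7% |
| 0.7 | 26.2% | 35.8% | 35.2% |
| 0.9 | 15.0% | 45.2% | 44.8% |

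**5. Other choices that keep the level.** A within-patient correlation using all readings gave 4.9% to 5.3%. Pooling with ICC 0.7 in one variable and 0 in the other gave 4.9%. Eight tests at 0.05/8 = 0.00625 gave 2.3% to 5.1% per pair. One value per patient is thus not the only route to 5%.

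**6. Which reading the plan makes.** The 0.05 rule applies to each p-value, so steps 1 and 2 describe what is written. Step 3 needs a per-pair standard that the plan does not state. Step 4 needs an analysis that the plan does not describe.

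**The case for a change.** The strongest reply is that silence is itself the weakness. Correcting the name still leaves pairs, times and unit of analysis open. Seven variables give 7 × 6/2 = 21 pairs, and one independent test of each would give 1 − 0.95^21 = 66% for at least one hit. No primary outcome is named and the correlations are not labelled exploratory, so nothing tells the reader to discount an isolated result. Naive pooling could also be worse than the table shows. With both variables shifted one SD down at T₀ and one SD up at T₇, and no other link between them, the pooled test rejected in 99% of 5,000 runs.

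What stands is that the sentence is thin and mislabelled, and that a reader of the results should look for the coefficient, the pairs, the times and the number of tests. What does not stand is treating the large percentages as the size of a fault in this plan. They measure analyses that it does not propose, at ICCs that it does not give. Whether a set of descriptive correlations needs familywise control is a matter of preference. An analyst who uses one value per patient, or a repeated-measures method, and reports which was used stays within the text as written.

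**Conclusion.** No change follows. The name is a clerical slip. Since the section otherwise compares groups with a t-test, ordinary Pearson is the likely meaning, though Spearman would serve as well: each holds about 5% on one value per patient, and under the null they differ in about 3% of datasets. The missing pairs and time points are routine detail that can be settled at analysis and disclosed in the report.

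The higher rates (15% to 34% for any of eight times, 12% to 45% for pooling) are conditional on choices that the plan does not make and on assumed ICCs of 0 to 0.9 for the first and 0.3 to 0.9 for the second. They are reasons to read a reported correlation with care. The comparison of Group L with Group N, which answers the trial's question, does not depend on any of this.

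### No primary rSO2 comparison, decision rule or multiplicity control is set for the title question, although rSO2 is recorded on two sides at eight times

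*Combined protocol and SAP*

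**What the plan says.** The title poses one question: "Does Low Flow Anesthesia Affect Cerebral Oxygenization in Bariatric Surgery". The Study Protocol section lists rSO2 alongside heart rate, SpO2, EtCO2, MAP and BIS: "left regional cerebral oxygen saturations (LrSO₂) and right regional cerebral oxygen saturations (RrSO₂) will record at before anesthesia (T₀), after intubation (T₁"), continuing through "after desufflation of CO₂ (T₆), after awakening from anesthesia (T₇"). That is two sides at eight times.

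On when the arms differ, the same section says "Initially, anesthesia maintain with desflurane inhalation with a flow of 2 L/min in 0.5 O₂ oxygen-air mixture in both groups". Only later, once the MAC target is met and "BIS values are 40-60 concurrently, the flow rate adjust to 0.75 L/min in Group L and 1.5 L/min in Group N", do the flows separate.

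The Statistical Analysis section consists of the software, "T-test and Chi-Square Test will be used for the comparison between groups", a correlation analysis, and "Value of p below 0.05 will be considered as statistically significant". No outcome, side, time point or summary is attached to the t-test or to the threshold. On size, the protocol says only "This study will perform in 60 adult patients".

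**The concern.** A threshold of 0.05 is conventional and valid for one test. What is missing is the rule that turns several rSO2 tests into one answer. Suppose the left side gives p=0.04 at T4 and nothing else is significant. One team could report that low flow affects cerebral oxygenation; another could require both sides to agree and report that it does not. Both would have followed the plan. The claim at risk is the trial's only stated question, and a rule chosen after the results are known cannot credibly repair it.

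**Working it through.** **1. Inputs from the document.** 60 patients; two sides; eight times; threshold 0.05; t-test. The plan gives no sample-size calculation or error rate for the rSO2 family, so there is no figure of its own to reproduce.

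**2. Inputs assumed, because the document is silent.** 30 per arm; two-sided tests; no true effect; normal data; correlation between times 0.5, 0.7 or 0.8 (either equal for all pairs of times or decaying as AR(1)); left-right correlation 0.7 or 0.85. This makes 12 scenarios.

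**3. Which readings can show a flow effect.** The full count is 2 × 8 = 16, but it overstates the problem.
- T0 is before anesthesia.
- T1 probably precedes the split, since both arms begin at the same flow.
- T7 follows awakening, when the assigned flow has presumably ended.
- T2 to T6 remain: 2 × 5 = 10 tests. T2 itself is uncertain, because the flow change depends on MAC and BIS targets rather than on a time point.

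**4. Upper reference, independent tests.** The chance of at least one false positive is 1 − 0.95^m. For m=10 it is 1 − 0.95^10 = 0.401; for m=12 (T2 to T7) it is 1 − 0.95^12 = 0.460.

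**5. Correlated tests.** Simulation with 40,000 null trials per scenario; ranges are the minimum and maximum over the 12 scenarios.

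| Rule for answering yes | T2–T6 | T3–T6 | T2–T7 |
|---|---|---|---|
| Any single p<0.05 | 0.188–0.319 | 0.168–0.270 | 0.204–0.367 |
| Both sides p<0.05, same direction, at one time | 0.048–0.107 | 0.042–0.086 | 0.053–0.128 |
| That pattern at two consecutive times | 0.006–0.024 | not run | 0.007–0.030 |

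With near-duplicate readings (time 0.9, left-right 0.95), the any-test rule still gives 0.129 to 0.149 for T2–T6 and 0.137 to 0.167 for T2–T7. Allocation of 25/35 or 20/40, run at the lowest and highest scenarios, gives 0.185–0.188 and 0.318–0.321 for T2–T6, so the range is essentially unchanged.

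**6. Does the proposed remedy control the error?** On the same scenarios, one ANCOVA on the two-side T2–T6 mean, adjusted for the T0 mean, has type I error 0.048 to 0.051. Holm over the ten separate tests has familywise error 0.027 to 0.043.

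**7. Power of the remedy.** Let r be the time correlation and s the left-right correlation. With equal correlation over time, the residual variance after T0 adjustment, in units of a single reading's variance, is (1+s)/2 × [(1+4r)/5 − r²].
- For r=0.8, s=0.7: 0.85 × (0.84 − 0.64) = 0.17, so the residual SD is 0.41, the smallest in the grid.
- The largest is 0.71 (AR(1), r=0.7, s=0.85).

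The noncentrality is d / (SD × √(2/30)), with 57 degrees of freedom.
- Sustained 0.5 SD difference: at SD 0.708, 0.5 / (0.708 × 0.258) = 2.74, power 0.767; at the smallest SD, power 0.996. One unadjusted t-test on one side at one time has 0.5 / 0.258 = 1.94, power 0.478.
- A 0.75 SD difference at only one of the five stages shifts the average by 0.75 / 5 = 0.15 SD: power 0.127 to 0.283, against 0.815 for a t-test at that stage.

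**The case against.** The strongest reply is that the plan never says a t-test will be run on each side at each time, nor that one significant result settles the matter. The 19% to 32% range belongs to the most permissive reading; a demand for both sides at two consecutive times would put the error well under 5%. That is correct: an inflated error rate is not proven. What is proven is that no rule is fixed, and the reply relies on a strict rule that the plan does not contain.

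The correlations, allocation, sidedness and time window are indeed assumed, so the size is illustrative. The direction is firm only under the any-test rule, where every scenario examined gave at least about 13%.

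The power contrast is also not like for like. The gain from 48% combines averaging, baseline adjustment and an assumed sustained effect; naming a single side and time would close the gap without that gain. ANCOVA and Holm are therefore examples, and only naming one comparison is essential.

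Finally, controlling false positives does not license reading a non-significant result as no effect; the plan gives no margin for that. This limit stands, and the remedy here does not remove it.

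**Conclusion.** The concern holds and should be fixed before analysis. The omission is plain from the text: nothing in either section identifies the rSO2 comparison that answers the title question or limits the number of chances to find one. The false-positive risk for that answer is undefined. Over T2 to T6 it runs from about 1% to 2% under the strictest rule examined, through 5% to 11% if both sides must agree at one time, to 19% to 32% if any single p<0.05 counts. Across near-duplicate to fully independent tests, the any-test figure spans 13% to 40%. These sizes depend on the assumptions listed above; the missing rule does not.

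**What to change.** Add to the Statistical Analysis section one primary rSO2 comparison, tested at two-sided 0.05. A suitable example is the mean of left and right rSO2, averaged over a fixed set of intra-operative time points after the flow change, compared between Group L and Group N by ANCOVA adjusted for T0. The set should be the same for every patient and should state whether T2 and T7 are in or out. A single named time point, or a repeated-measures model with one named contrast, would serve equally well to close the gap. Report per-side and per-time rSO2 results as secondary, either Holm-adjusted or labelled exploratory.

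The cost is a few sentences; T0 and both sides are already recorded, and no extra patients are needed. Two things are given up. Isolated time-point p-values can no longer be claimed as findings, and an averaged measure has low power for a brief effect confined to one stage. If such an effect is the real target, that stage should be named as primary instead.
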